7.2. Norfolk Quality of Life-Diabetic Neuropathy (Norfolk QOL-DN).....	32
7.3. EuroQOL-5-Dimension 5-Level (EQ-5D-5L).....	32
7.4. Rasch-Built Overall Disability Scale (R-ODS).....	33
7.5. Composite Autonomic Symptom Score-31 (COMPASS-31).....	33

LIST OF ABBREVIATIONS AND DEFINITION OF TERMS

Abbreviation	Definition
Σ5	sum of 5 nerve conduction attributes
ADA	anti-drug antibody
AE	adverse event
ALP	alkaline phosphatase
ALT	Alanine aminotransferase
AST	Aspartate aminotransferase
ATC	anatomic therapeutic class
BMI	body mass index
C-SSRS	Columbia-Suicide Severity Rating Scale
CSR	clinical study report
COMPASS-31	Composite Autonomic Symptom Score
eCRF	electronic case report form
CRO	contract research organization
eGFR	estimated glomerular filtration rate
ELISA	enzyme linked immunosorbent assay
EQ-5D-5L	EuroQoL five dimensions, five-level scale
EQ-VAS	EuroQoL visual analog scale
EW	early withdrawal
FAP	familial amyloidotic polyneuropathy
hATTR	hereditary transthyretin-mediated amyloidosis
HLT	high level term
HP	heat pain
HRdb	heart rate response to deep breathing
ICH	International Conference on Harmonisation
IENFD	intraepidermal nerve fiber density
INN	International Nonproprietary Name
IRR	infusion-related reaction
IV	intravenous
KPS	Karnofsky performance status
LOCF	last observation carried forward
mBMI	modified body mass index
MedDRA	Medical Dictionary for Regulatory Activities
mNIS+7	Modified Neuropathy Impairment Score

Abbreviation	Definition
MR	magnetic resonance
NCS	nerve conduction studies
NIS	Neuropathy Impairment Score
NIS+7	Neuropathy Impairment Score + sum of 7 nerve tests
NIS-W	Neuropathy Impairment Score - Weakness
NT-proBNP	N-terminal prohormone of B-type natriuretic peptide
NYHA	New York Heart Association
PBP	postural blood pressure
PD	pharmacodynamic
PND	polyneuropathy disability
PT	preferred term
QOL	quality of life
QOL-DN	Quality of Life-Diabetic Neuropathy
QST	quantitative sensory testing
R-ODS	Rasch-built Overall Disability Scale
SAE	serious adverse event
SAP	statistical analysis plan
SD	standard deviation
SGNFD	sweat gland nerve fiber density
siRNA	small interfering ribonucleic acid
SMQ	Standardized MedDRA query
SOC	system organ class
TP	touch pressure
TTR	transthyretin
ULN	upper limit of normal
V30M	Val30Met
VDT	vibration detection threshold
WHO	World Health Organization
WT	wild type

1. INFORMATION FROM THE STUDY PROTOCOL

1.1. Introduction and Objectives

1.1.1. Introduction

Patisiran (the International Nonproprietary Name [INN] for the drug product also referred to as ALN-TTR02) is a novel investigational agent being developed for the treatment of polyneuropathy in patients with hereditary transthyretin-mediated (hATTR) amyloidosis. Patisiran comprises a small interfering ribonucleic acid (siRNA) which is specific for transthyretin (TTR), and is formulated in a hepatotropic lipid nanoparticle (LNP) for intravenous (IV) administration.[1] It is designed to significantly suppress liver production of both wild type (WT) and all mutant forms of TTR, thereby having the potential to reduce amyloid formation and provide clinical benefit to patients with hATTR amyloidosis.

ALN-TTR02-006 (hereinafter referred to as study 006) is a multicenter, open-label extension study designed to evaluate the long-term safety and efficacy of patisiran in patients with hATTR amyloidosis with polyneuropathy who have completed a prior study with patisiran (ALN-TTR02-003 or ALN-TTR02-004, hereinafter referred to as Studies 003 and 004, respectively).

1.1.2. Document and Study Objectives

This statistical analysis plan (SAP) is designed to outline the methods to be used in the analysis of study data in order to address the study objectives of Study 006. Populations for analysis, data handling rules, statistical methods, and formats for data presentation are provided. The statistical analyses and summary tabulations described in this SAP will provide the basis for the results sections of the clinical study report (CSR) for this trial.

This SAP will also outline any differences in the currently planned analytical objectives relative to those planned in the study protocol and will be used to guide the interim and final analyses of the study.

The objective of this study is to assess the safety and efficacy of long-term dosing with patisiran in patients with hATTR amyloidosis with polyneuropathy.

1.2. Study Design

1.2.1. Synopsis of Study Design

This is a multicenter, multinational, open-label extension study to evaluate the long-term safety and efficacy of patisiran in patients with hATTR amyloidosis with polyneuropathy who have previously completed a patisiran study.

Consented eligible patients will enroll in this study and receive 0.3 mg/kg patisiran IV once every 21 days for the duration of the study. The study inclusion and exclusion criteria are listed in Sections 4.1 and 4.2 of the study protocol. All dosing visits have a window of ± 3 days. In order to maintain the 21-day dosing schedule from the parent study, patients are expected to have their first visit (Day 1) on this study 3 weeks after their last dosing visit on the parent study. However, a patient may initiate dosing in this study up to 45 days from the time of the last dose in the parent study. The last testing visit in the parent study will serve as the baseline for this study, unless more than 45 days have elapsed, in which case the baseline tests will be repeated prior to the first dose of patisiran on Day 1. Eligibility for this study will be confirmed before administration of the first dose on Day 1.

After the Day 1 visit, patients will either return to the clinical site for the patisiran infusions or will receive the patisiran infusions at home once every 21 (± 3) days. Patients who are receiving patisiran infusions at home will have phone contact with the site at least every 30 (± 5) days. Patients will also have visits at the clinical site at approximately 26 and 52 weeks, and yearly thereafter.

A complete set of efficacy assessments will be performed at 52 weeks (± 4 weeks), followed by more limited efficacy assessments yearly thereafter.

Safety will be assessed throughout the study. Patients will return to the clinical site for safety evaluations at 26 and 52 weeks during the first year and yearly thereafter. Patients will be continually assessed throughout the study for adverse events (AEs). Unscheduled visits for study assessments may occur if deemed necessary by the study personnel.

Patients rolling over into this open-label study from a previously blinded study will remain blinded to their previous treatment assignment until after database lock has occurred in that parent study.

1.2.2. Study Procedures

The schedule of assessments is presented in Table 1 of the study protocol.

1.2.3. Efficacy, Pharmacodynamic, Safety, and Other Assessments

1.2.3.1. Efficacy Assessments

The efficacy of patisiran will be evaluated using the following assessments:

- Neurological impairment assessed using the Neuropathy Impairment Score (NIS), Modified NIS (mNIS +7) composite score and NIS+7.
- Patient reported quality of life (QOL) using the EuroQoL five dimensions, five-level scale (EQ-5D-5L) questionnaire and the Norfolk Quality of Life –Diabetic Neuropathy (QOL-DN) questionnaire; patients from Study 003 do not have to complete the Norfolk QOL-DN questionnaire.
- Overall health using the EuroQoL visual analog scale (EQ-VAS).
- Disability reported by patients using the Rasch-built Overall Disability Scale (R-ODS).
- Autonomic symptoms assessed using the Composite Autonomic Symptom Score (COMPASS-31).
- Motor function assessments, including timed 10-meter walk test and grip strength test.
- Polyneuropathy disability (PND) score and familial amyloidotic polyneuropathy (FAP) stage.
- Nutritional status using modified body mass index (mBMI).
- Pathologic evaluation of sensory and autonomic innervation evaluated by intraepidermal nerve fiber density (IENFD) analysis and quantitation of dermal sweat gland nerve fibers (SGNFD) via tandem 3mm skin punch biopsies taken from the leg (only for patients having this assessment in the parent study).
- Dermal amyloid content (% Congo Red staining) using the same skin punch biopsy specimens analyzed for nerve fiber density.

- Magnetic resonance (MR) neurography (in Germany and France only).
- Cardiac assessment with echocardiograms and serum levels of terminal prohormone of B-type natriuretic peptide (NT-proBNP) and troponin I.
- New York Heart Association (NYHA) classification of heart failure.

1.2.3.2. Pharmacodynamic Parameters and Pharmacology Parameters

Pharmacodynamic (PD) markers include serum TTR assessed using enzyme linked immunosorbent assay (ELISA) and vitamin A.

Blood will be collected to evaluate anti-drug antibodies (ADA).

1.2.3.3. Safety Parameters

Safety evaluations performed during the study include monitoring of AEs and concomitant medications, physical examinations, measurement of vital signs, clinical laboratory evaluations (including hematology, clinical chemistry [including liver function tests and thyroid stimulating hormone], urinalysis, and pregnancy testing), and ophthalmology examinations.

Suicidal ideation and behavior will be assessed using the Columbia–Suicide Severity Rating Scale (C-SSRS) questionnaire.

1.2.3.4. Other Parameters

Disease burden and healthcare utilization will be assessed using a patient reported pharmacoeconomics questionnaire.

2. PATIENT POPULATION

2.1. Population Definitions

The following patient populations will be evaluated and used for presentation and analysis of the data:

- Full Analysis Set: All patients who were enrolled will be included in the full analysis set. The full analysis set will be the primary set for the analysis of efficacy data.
- Pharmacodynamic (PD) Analysis Set: All patients who received at least 1 dose of patisiran in this study and have both baseline and at least 1 post-baseline PD assessment (either TTR or Vitamin A). For a patient who received patisiran in the parent study, if more than 45 days elapsed between the last dose of patisiran in the parent study and the first dose of patisiran in this study, the patient will be excluded from the PD analysis set.
- Safety Analysis Set: All patients who were enrolled and who received at least 1 dose of patisiran in this study. The safety analysis set will be used for the analysis of safety data.

2.2. Protocol Deviations

A deviation is considered any departure from the procedures set forth in the protocol. Protocol deviations will be classified into major and minor by medical review. A major deviation includes any deviation that may impact patient safety or efficacy interpretation. Deviations not designated as major will be considered minor.

All protocol deviations and major protocol deviations will be presented in separate data listings.

3. GENERAL STATISTICAL METHODS

3.1. Sample Size Justification

This is an open-label extension study enrolling patients who have previously completed a patisiran clinical study (Study 004 or 003); the size of the study is not determined via power analysis of particular hypotheses tests.

3.2. General Methods

As this is an extension study, formal statistical hypothesis testing will not be performed. All summaries are descriptive.

All data will be presented in by-patient data listings. The listings that contain an evaluation date will include 2 study days as described below:

- 1) Extension study day: the study day relative to the first dose date of patisiran in this study. The first dose date is designated as Day 1. On-treatment study days will be calculated as evaluation date – first dose date +1 and pre-treatment days will be calculated as evaluation date – first dose date. For example, the day prior to the first dose of patisiran will be Day -1 and the day after the first dose of patisiran will be Day 2, etc.
- 2) Parent study day: the study day relative to the day of the first dose of study drug in the parent study (Study 004 or 003).

All output will be incorporated into Microsoft Word files, sorted and labeled according to the International Conference on Harmonisation (ICH) recommendations, and formatted to the appropriate page size(s).

For categorical variables, summary tabulations of the number and percentage of patients within each category (with a category for missing data) of the parameter will be presented. For continuous variables, the number of patients, mean, median, standard deviation (SD), minimum, and maximum values will be presented.

Laboratory data (including vitamin A) collected and recorded as below the limit of detection will be set equal to the lower limit of detection for the calculation of summary statistics.

For assessments with planned repeat assessments at a given study visit (e.g., 10-meter walk tests), the average will be calculated unless otherwise noted.

All data recorded on the eCRF will be included in data listings.

3.3. Computing Environment

All descriptive statistical analyses will be performed using SAS statistical software Version 9.3 (or later), unless otherwise noted. Medical history and AEs will be coded using the Medical Dictionary for Regulatory Activities (MedDRA) version 18.0 (or later). Concomitant medications will be coded using the World Health Organization (WHO) Drug Dictionary version March 2015 (or later).

3.4. Baseline Definitions

Unless noted otherwise, baseline will be defined as the last non-missing measurement on or prior to the first dose of patisiran in this study. For several procedures, the last testing visit in the parent study will serve as the baseline for this study, unless more than 45 days have elapsed, in which case the test will need to be repeated on Day 1 in this study; see Table 1 of the study

protocol for additional details. If more than 45 days have elapsed and the assessment is not repeated on Day 1, the last assessment from the parent study will serve as baseline for this study; any such occurrence will be identified as a protocol deviation.

For the mNIS+7/NIS+7 individual components, total scores and related endpoints, grip strength test, and 10-meter walk test, baseline will be calculated as the average of 2 replicates.

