3.5. Study Group

Data from all sites will be summarized together. Patients will be grouped into the following 3 study groups:

- 1) 004 Placebo: patients in Study 006 who previously received placebo in Study 004.
- 2) 004 Patisiran: patients in Study 006 who previously received patisiran in Study 004.
- 3) 003 Patisiran: patients in Study 006 who previously received patisiran in Study 003.

Summary tables and figures will include presentations by study group and overall.

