4.4. Pharmacodynamic Analyses

Pharmacodynamic analyses will be based on the PD analysis set.

The PD parameters include serum TTR (ELISA) and vitamin A. All summary tables and figures will be based on assessments within 21 days of last dose of patisiran. Assessments more than 21 days after last dose will be presented in listings and individual patient plots only.

Summary tables will be provided for observed values, changes and percentage changes from baseline for each scheduled time point by study group and overall. Graphical displays will be provided for the observed values of TTR and vitamin A for each scheduled time point by study group.

All PD data will be displayed in data listings.

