- If no single complete mNIS+7 measure can be found or recovered, mNIS+7 score is considered as missing.

In 006, if the last mNIS+7 assessment in the parent study was done more than 45 days before the first dose in 006, mNIS+7 will be reassessed on Day 1 in 006. It is expected that very few patients will have this Day 1 assessment; therefore, the imputation algorithm for missing components in mNIS+7 will be slightly different from the general algorithm. If NIS-W is missing from both replicates, the mNIS+7 total score will be considered as missing, similar to the general algorithm. If any other component is missing from both replicates, the component score will be imputed by last observation carried forward (LOCF) using the imputed average component score from the last assessment in the parent study.

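### The single Study 006 baseline is an on-drug value for two of the three groups, so their change tables show maintenance only, and the overall change column depends on group mix

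*SAP*

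**What the plan says.** SAP Section 3.4 sets one general rule for every patient: "baseline will be defined as the last non-missing measurement on or prior to the first dose of patisiran in this study". It adds a further sentence, quoted here as far as its time limit: "For several procedures, the last testing visit in the parent study will serve as the baseline for this study, unless more than 45 days have". Section 1.2.1 says what happens after a longer gap: "in which case the baseline tests will be repeated prior to the first dose of patisiran on Day 1". Section 7.1.1.1 treats that as rare for mNIS+7: "It is expected that very few patients will have this Day 1 assessment".

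Section 3.5 forms three groups by earlier treatment. One starts patisiran in Study 006 ("004 Placebo: patients in Study 006 who previously received placebo in Study 004"). The other two continue it: "004 Patisiran: patients in Study 006 who previously received patisiran in Study 004", and the corresponding group from Study 003.

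Section 4.4 plans the PD tables: "Summary tables will be provided for observed values, changes and percentage changes from baseline for each scheduled time point by study group and overall". Section 4.5 plans observed values and changes for the efficacy endpoints, again by group and overall.

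The objective in Section 1.1.2 is to "assess the safety and efficacy of long-term dosing with patisiran".

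**The concern.** For a patient who took patisiran in Study 003 or 004, the value that serves as the 006 baseline was obtained on treatment. A percentage change in TTR or vitamin A from that value shows whether suppression has held. It does not show how large the suppression is. A change in mNIS+7 or COMPASS-31 from that value likewise leaves out whatever happened during the parent study.

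For 004 Placebo patients the same column heading means change since before patisiran. Two different quantities therefore share one label, and the overall column averages them.

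What is at stake is the reading of the report. These tables are the basis for the CSR results (Section 1.1.2), and interim versions are meant for regulatory use and publication (Section 3.12). The patients with the longest exposure bear most directly on the objective, yet no change table covers their full time on drug.

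**Working it through.** The SAP states no sample size, group size, expected suppression or expected score change, so it has no figure of its own to reproduce. The check sets the sections side by side and then illustrates the pooling.

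**Is the baseline on drug for the continuing groups?**

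- Section 1.2.1 aims to keep the 21-day dosing rhythm. Day 1 is expected 3 weeks after the final parent-study dosing visit and may follow the last parent dose by up to 45 days.
- Section 3.4 takes the baseline for several procedures from the last parent-study testing visit. If a required Day 1 repeat is not done, the parent value is still used.
- Section 2.1 removes from the PD analysis set any prior-patisiran patient with more than 45 days between the last parent dose and the first 006 dose. Those who remain had patisiran recently.

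So, apart from the few patients with a long gap, the baseline in the 004 Patisiran and 003 Patisiran groups is an on-drug value.

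**Is another baseline defined?** No. Section 3.2 defines a study day counted from the first parent-study dose, but only for listings. Sections 3.4, 4.4 and 4.5 name no pre-patisiran value.

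**What does the overall column average?** Let p be the share of 004 Placebo patients, K the percentage reduction in TTR from the pre-patisiran level, and suppose continuing patients stay level in 006.

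- From the 006 baseline: overall change = p × (-K) + (1 - p) × 0 = -K × p.
- From a pre-patisiran baseline: overall change = p × (-K) + (1 - p) × (-K) = -K, whatever p is.

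Both K and p are assumptions:

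| K | p = 0.10 | p = 0.25 | p = 0.50 | From pre-patisiran baseline |
|---|---|---|---|---|
| 60% | -6% | -15% | -30% | -60% |
| 80% | -8% | -20% | -40% | -80% |
| 90% | -9% | -22.5% | -45% | -90% |

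For a score, assume a mean change of -5 in starters and +5 in continuing patients. The overall mean is p × (-5) + (1 - p) × 5:

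- p = 0.10: -0.5 + 4.5 = +4.0
- p = 0.25: -1.25 + 3.75 = +2.5
- p = 0.50: -2.5 + 2.5 = 0.0

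**Is p the same in every table?** Not necessarily. Study 003 patients need not complete the Norfolk QOL-DN (Sections 1.2.3.1 and 4.5). Nerve fiber density biopsies are limited to patients who had them in the parent study (Section 1.2.3.1). The 45-day PD exclusion applies only to prior-patisiran patients (Section 2.1). Overall columns for different endpoints can therefore average different mixes.

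**Percentage change from a suppressed value.** A swing equal to 5% of the pre-patisiran level, expressed against the on-drug baseline, is 5 / (100 - K) × 100:

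- K = 60: 5 / 40 = 12.5%
- K = 80: 5 / 20 = 25%
- K = 90: 5 / 10 = 50%

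A small absolute movement can thus look large in the continuing groups.

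**The case against.** The case for leaving the plan alone is substantial, and most of it stands.

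- **The 006 baseline is a legitimate choice.** Whether benefit is maintained in treated patients is itself a question about long-term dosing, and change from the 006 baseline answers it. The PD exclusion suggests that continuous treatment at baseline was intended. This stands.
- **Groups are shown separately.** Sections 3.5, 4.4 and 4.5 give each group its own results, and the TTR and vitamin A graphs in Section 4.4 are specified by study group. Nobody has to rely on the overall column. This stands, but it does not supply the missing change from before patisiran.
- **Observed values are tabulated too.** The level of TTR or of a score in treated patients can be read beside the 004 Placebo baseline. This stands. It is a comparison between groups, however, and not the within-patient change.
- **Everything is descriptive.** Section 3.2 plans no hypothesis tests, so no inference is biased. This limits the weight of the point, but a descriptive mean still needs a clear reference.
- **A pooled column from a pre-patisiran baseline would also be a mixture.** At a given 006 visit, 004 Placebo patients have been on patisiran for less time than the others. This is correct, and the fix allows for it.

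A reader might infer that everyone's baseline is a value measured on Day 1 of the extension. Sections 1.2.1, 3.4 and 7.1.1.1 do not support that: for several procedures the parent-study visit is the rule and Day 1 retesting the exception. The consequence does not change, because that parent visit is also on drug for the continuing groups.

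**Conclusion.** The point holds in a limited form. One 006 baseline serves all groups, it is an on-drug value for two of the three, and no pre-patisiran baseline is defined. For those two groups the change tables therefore cover maintenance in 006 only, and the overall change column depends on how many patients each group contributes.

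Two stronger conclusions do not follow. One is that the planned tables cannot show anything about long-term dosing; by-group changes and observed values do show part of it. The other is that the overall column has no meaning. It is the mean change during 006 among the patients analysed, but it is easily misread as a treatment effect.

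The size cannot be fixed from the SAP. With suppression of 60% to 90% and a 004 Placebo share of 10% to 50%, the overall TTR change could lie anywhere from -6% to -45%, while every patient sits 60% to 90% below the pre-patisiran level. These figures rest on assumed K and p, the same K in all patients, and continuing patients who stay level. This is a worthwhile improvement to how the plan serves its objective. It is not an internal contradiction.

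**What to change.** 1. In Section 3.4, define a second, labelled pre-patisiran baseline. For patients treated with patisiran in Study 003 or 004 it is the parent-study baseline. For 004 Placebo it is the 006 baseline.
2. In Sections 4.4 and 4.5, tabulate change from this baseline, and percentage change for PD, by study group beside the 006-baseline results. Limit this to endpoints that were measured in the parent study.
3. State in each table title which baseline is used.
4. Footnote or omit the overall column for change from the 006 baseline. If an overall column is shown for the pre-patisiran baseline, state that time on patisiran differs between groups.

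The cost is SAP wording, extra table columns and bringing parent-study baseline data into the 006 analysis datasets. The SAP already draws on parent-study values for its baseline. No new assessment of patients is needed.
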